11.2. Standard data derivation

11.2.1. Date derivation

- SAS date derived from a character date: In case day is missing, 15 is used. In case day & month are missing, 30 June is used.
- Onset day for an event for the infant (AE, medication, vaccination, ...): The onset day is the number of days from date of last study dose & the onset/start date of the event. This is 0 for an event starting on the same day of last study dose. There could also be events reported in the infant before delivery (anomalies diagnosed during pregnancy at ultrasound investigation), for these cases onset day will be negative ‘-‘ days. See SAS date derived in case the start date of the event is incomplete.
- Duration: Duration of an event is expressed in days. It is the number of days between the start & the stop dates + 1. Therefore duration is 1 day for an event starting & ending on the same day.

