- The verbatim reports of unsolicited AEs will be reviewed by a physician and the signs and symptoms will be coded according to MedDRA. Every verbatim term will be matched with the appropriate Preferred Term. The percentage of subjects with unsolicited AEs occurring within 31-day (Day 0- Day 30) follow-up period after any dose with its exact 95% CI [Clopper, 1934] will be tabulated by group, and by preferred term. Similar tabulation will be done for unsolicited AEs rated as grade 3, for unsolicited AEs with causal relationship to vaccination and AEs/SAEs leading to withdrawal from the study.
- The percentage of subjects who receive concomitant medication and antipyretic medication during the 4-day (Day 0- Day 3) follow-up period and the 31-day follow-up (Day 0 – Day 30) will be tabulated (with exact 95% CI [Clopper, 1934]) after each vaccine dose and overall.
- SAEs reported from first vaccination dose up to study end will be described in detail.
- Withdrawal due to AEs and SAEs following vaccinations will be described in detail.

Handling of missing data:

- For a given subject and the analysis of solicited AEs 4 days post-vaccination, missing or non-evaluable measurements will not be replaced. Therefore, the analysis of the solicited AEs based on the TVC will include only vaccinated subjects and doses with documented safety data (i.e. symptom screen completed).
- For analysis of unsolicited AEs, such as SAEs or AEs by primary Medical Dictionary for Regulatory Activities (MedDRA) term, and for the analysis of concomitant medications, all vaccinated subjects will be considered. Subjects, who do not report the event or the concomitant medication, will be considered as subjects without the event or the concomitant medication, respectively.
- For summaries reporting both solicited and unsolicited AEs, all vaccinated subjects will be considered. Subjects, who do not report the event or the concomitant medication, will be considered as subjects without the event or the concomitant medication, respectively.

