11.2.2. Dose number

The study dose number is defined in reference to the number of study visits at which vaccination occurred. More specifically dose 1 refers to all vaccines administered at the first vaccination visit while dose 2 corresponds to all vaccinations administered at the second vaccination visit even if this is the first time a product is administered to the subject.

Relative dose: the relative dose for an event (AE, medication, vaccination) is the most recent study dose given before an event. In case the event takes place on the day a study dose is given, the related dose will be that of the study dose, even if the event actually took place before vaccination. For instance, if an adverse event begins on the day of the study vaccination but prior to administration of the vaccine, it will be assigned to this dose. In case a study dose is not administered and an event occurs after the subsequent study dose (e.g. 3rd study dose), the relative dose of the event will be study dose associated to the subsequent study dose (e.g. dose 3).

The number of doses for a product is the number of time the product was administered to a subject.

The incidence per dose is the number of vaccination visits at which an event (vaccination visit is a visit at which study vaccine was administered) was reported among all vaccination visits.

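### Partial AE and medication start dates are imputed without reference to the dose date, so some post-vaccination events can leave the 31-day window or go to the wrong dose

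*SAP*

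**What the plan says.** SAP 11.2.1 gives one rule for partial dates: "In case day is missing, 15 is used. In case day & month are missing, 30 June is used". The same section defines onset day for AEs, medications and vaccinations: "The onset day is the number of days from date of last study dose & the onset/start date of the event". For incomplete start dates it points back to the rule: "See SAS date derived in case the start date of the event is incomplete". SAP 11.2.2 then assigns the dose: "the relative dose for an event (AE, medication, vaccination) is the most recent study dose given before an event".

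The derived dates decide who enters the windowed tables in SAP 6.4.1. These report "The percentage of subjects with unsolicited AEs occurring within 31-day (Day 0- Day 30) follow-up period after any dose", and medication use "during the 4-day (Day 0- Day 3) follow-up period and the 31-day follow-up", the latter after each dose and overall. Subjects stay in the denominator whether or not an event is counted: "Subjects, who do not report the event or the concomitant medication, will be considered as subjects without the event or the concomitant medication, respectively".

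Protocol 8.2.1 has AEs recorded when they start on Day 0-30 after a dose. Neither document bounds an imputed date by the dose, birth or visit date.

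**The concern.** A non-serious AE is collected because it began within 30 days of a dose, so a partial start date on such a record is already known to lie in a window. The imputation discards that knowledge.

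- **Imputed before the dose.** Dose on the 20th, AE on the 25th, day missing: the start becomes the 15th. At dose 1 the onset day is -5. At dose 2 with 60-day spacing the event attaches to dose 1 at day 60 - 5 = 55, outside the window. With 30-day spacing it becomes day 25 of the wrong dose.
- **Imputed after Day 30.** Dose on 3 April, AE on 2 May (Day 29), day missing: the start becomes 15 May, Day 42.
- **Day and month missing.** First dose on 10 September at 60 days of age (born 12 July), AE on 14 September, only the year known: the start becomes 30 June, before birth.

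An event moved out of every window is not counted unless the subject has another qualifying event. All analyses are descriptive, so the tabulated percentages are themselves the safety result.

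**Working it through.** The plan states no misclassification figure, so there is nothing to reproduce. The check applies the rule as written to events that truly start in a window.

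**Inputs from the documents**
- Imputation, onset-day and relative-dose rules: SAP 11.2.1 and 11.2.2.
- Window Day 0-30: SAP 6.4.1.
- Dose spacing: 52-78 days (60 used) for 2-4-6 and the two-dose schedules, 21-48 days (30 used) for 2-3-4; protocol Tables 6 to 9.
- Schedule mix, SAP 6.3.2: 457 subjects on 2-4-6, 71 on 2-3-4, and 7 + 66 = 73 on two doses; 601 in all.

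**Assumptions not in the documents**
- First-dose dates uniform over a four-year calendar cycle (1,461 days).
- Onset uniform over Day 0-30, then varied.

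**Own-dose window, day missing.** Measure in months, with dose at position d and onset at d + u, both d and u uniform on 0 to 1.
- Imputed before the dose: d > 1/2 and u < 1 - d, probability 1/8.
- Imputed after Day 30: d < 1/2 and u > 1 - d, probability 1/8.
- Sum: 25%. Exact enumeration gives 13.5% + 11.1% = 24.6%.

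**Own-dose window, day and month missing.** 1 - 31/365 = 91.5%; enumeration agrees.

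**Any-dose window.** Here an event counts if it lands in the window of any dose.

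| Schedule (subjects × doses) | Day missing: lost | Day missing: in another dose's window | Day and month missing: lost | Day and month missing: in another dose's window |
|---|---|---|---|---|
| 2-4-6 (457 × 3 = 1,371) | 24.6% | 0% | 74.5% | 17.0% |
| 2-3-4 (71 × 3 = 213) | 8.4% | 16.8% | 75.1% | 16.6% |
| Two doses (73 × 2 = 146) | 24.6% | 0% | 83.0% | 8.5% |

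Weighted by doses (total 1,730):
- Day missing: (1,371 × 0.246 + 213 × 0.084 + 146 × 0.246) / 1,730 = 22.6%.
- Day and month missing: (1,371 × 0.745 + 213 × 0.751 + 146 × 0.830) / 1,730 = 75.3%.

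At the 48-day upper limit of spacing, the 2-3-4 loss with the day missing is also 24.6%.

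**Sensitivity to early onset, day missing** (exponential decay)

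| Mean onset | Own-dose loss | Weighted any-dose loss |
|---|---|---|
| 10 days | 30.2% | 27.7% |
| 5 days | 37.1% | 34.1% |
| 2 days | 45.7% | 41.9% |

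The weighted 30 June figure stays at 75.3% under every onset pattern, but it depends on when in the year vaccination took place.

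**Single-dose Day 0-3 medication window.** Day missing: 1 - 4/30.4 = about 87%. Day and month missing: 1 - 4/365 = about 99%.

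**Check of the alternative.** Impute the later of the dose date and the first day of the known month (or year). If the first of the month is later than the dose, it is still no later than the true onset, which is at most Day 30. Otherwise the imputed date is Day 0. So 0% of true in-window events leave their own dose's window, provided the right dose is identified.

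**The case against.** The strongest case against is materiality. These are shares of partially dated records, not of safety rates, and the documents do not say how many such records there are. Diary cards are verified with the parent at the next visit, missing cards are chased, data omissions are queried, and follow-up lasts 3 to 5 months. A diary-card AE known only by its year should be very rare. The main unsolicited table counts subjects, so one with another correctly dated event still appears in the at-least-one row. Solicited AEs come from daily recordings, and SAEs are tabulated from first dose to study end. All of this stands and keeps the point minor.

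A reader might infer two stronger conclusions.
- **That a missing day and month removes nearly all such events from the 31-day AE table.** The 91.5% applies to the event's own dose. The planned table counts any dose, where the loss is 74.5% to 83.0% by schedule.
- **That safety rates are biased downwards.** No reported rate can be shown to be biased without the number of partial dates, and an event that lands in another dose's window is still counted.

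That the rule is only a standard convention does not answer the point. Applied as written, it contradicts the window in which the AE was collected.

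**Conclusion.** The point holds as a minor defect in a derivation rule. The rule can under-count unsolicited AEs and medications with partial start dates, or attach them to the wrong dose. Per 100 AEs with only the day missing, about 23 would leave the any-dose table under uniform dates and 30-day spacing on the 2-3-4 schedule, and up to about 42 if onset averages 2 days. Per 100 with day and month missing, about 75 would leave it.

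These sizes rest on assumed calendar and onset patterns. The effect on any reported percentage is this share times the unknown, probably small, fraction of partial dates. The rule is identical in both groups, so the documents give no reason to expect a group difference from it.

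**What to change.** Amend SAP 11.2.1 for AE and medication start dates:

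1. When a partial start date is compatible with onset on or after a study dose, impute the later of that dose date and the first day of the known month, or of the known year if the month is missing.
2. Where more than one dose is compatible, use the dose whose post-vaccination period or visit the event was reported for. Failing that, use the most recent compatible dose before the reporting visit.
3. Drop the 30 June default for post-vaccination events.
4. Flag every event with an imputed date, and show the 4-day medication and symptom tables with and without flagged events.

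Taking the later of the 15th and the dose date would not be enough: it leaves the roughly 11% imputed beyond Day 30 where they are. A bare reference to the dose date is also undefined when several doses fall in one year.

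The cost is a few SAP sentences and modest programming. Step 2 needs a link from the record to a visit or diary card, and the documents do not say whether the database holds one. The statistical cost is that some later events move towards Day 0 and may enter the Day 0-3 tables, hence step 4. Medications are recorded continuously from Visit 1 to Visit 4 (protocol 6.7.1), so some that began after Day 30 could be drawn into the 31-day medication table; the same flag makes these visible.

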11.2.2. Dose number

The study dose number is defined in reference to the number of study visits at which vaccination occurred. More specifically dose 1 refers to all vaccines administered at the first vaccination visit while dose 2 corresponds to all vaccinations administered at the second vaccination visit even if this is the first time a product is administered to the subject.

Relative dose: the relative dose for an event (AE, medication, vaccination) is the most recent study dose given before an event. In case the event takes place on the day a study dose is given, the related dose will be that of the study dose, even if the event actually took place before vaccination. For instance, if an adverse event begins on the day of the study vaccination but prior to administration of the vaccine, it will be assigned to this dose. In case a study dose is not administered and an event occurs after the subsequent study dose (e.g. 3rd study dose), the relative dose of the event will be study dose associated to the subsequent study dose (e.g. dose 3).

The number of doses for a product is the number of time the product was administered to a subject.

The incidence per dose is the number of vaccination visits at which an event (vaccination visit is a visit at which study vaccine was administered) was reported among all vaccination visits.

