8.1. Safety definitions

8.1.1. Definition of an adverse event

An AE is any untoward medical occurrence in a clinical investigation subject, temporally associated with the use of a medicinal product, whether or not considered related to the medicinal product.

An AE can therefore be any unfavourable and unintended sign (including an abnormal laboratory finding), symptom, or disease (new or exacerbated) temporally associated with

the use of a medicinal product. For marketed medicinal products, this also includes failure to produce expected benefits (i.e. lack of efficacy), abuse or misuse.

Examples of an AE include:

- Significant or unexpected worsening or exacerbation of the condition/indication under study.
- New conditions detected or diagnosed after investigational vaccine even though they may have been present prior to the start of the study.
- Signs, symptoms, or the clinical sequelae of a suspected interaction.
- Signs, symptoms, or the clinical sequelae of a suspected overdose of either investigational vaccine or a concurrent medication (overdose per se should not be reported as an AE/SAE).
- Signs, symptoms temporally associated with vaccine administration.
- Significant failure of expected pharmacological or biological action.
- Pre- or post-treatment events that occur as a result of protocol-mandated procedures (i.e. invasive procedures, modification of subject's previous therapeutic regimen).

AEs to be recorded as endpoints (solicited AEs) are described in Section 8.1.3. All other AEs will be recorded as UNSOLICITED AEs.

Examples of an AE DO NOT include:

- Medical or surgical procedures (e.g. endoscopy, appendectomy); the condition that leads to the procedure is an AE/SAE.
- Situations where an untoward medical occurrence did not occur (e.g. social and/or convenience admission to a hospital, admission for routine examination).
- Anticipated day-to-day fluctuations of pre-existing disease(s) or condition(s) present or detected at the start of the study that do not worsen.
- Pre-existing conditions or signs and/or symptoms present in a subject prior to the first study vaccination. These events will be recorded in the medical history section of the eCRF.

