4.2. Secondary endpoints

- Persistence of antibodies before the first dose of *Infanrix hexa*.
 - Anti-diphtheria and anti-tetanus seroprotection status, anti-PT, anti-FHA, anti-PRN seropositivity status and antibody concentrations.
- Immunogenicity with respect to components of *Infanrix hexa* and Prevenar 13.
 - Anti-diphtheria, anti-tetanus, anti-poliovirus type 1, anti-poliovirus type 2, anti-poliovirus type 3, anti-HBs, anti-PRP, anti-PT, anti-FHA, anti-PRN and anti-pneumococcal serotypes (1, 3, 4, 5, 6A, 6B, 7F, 9V, 14, 18C, 19A, 19F, 23F) antibody concentrations or titres, one month after the last dose of primary vaccination.
- Immunogenicity with respect to components of *Infanrix hexa*.
 - Anti-PT, anti-FHA, anti-PRN antibody seropositivity status, one month after the last dose of primary vaccination.

- Solicited local and general symptoms.
 - Occurrence of solicited local/general symptoms during the 4-day (Day 0-Day 3) follow-up period after each vaccination.
- Unsolicited adverse events.
 - Occurrence of unsolicited symptoms during the 31-day (Day 0-Day 30) follow-up period after each vaccination.
- Serious adverse events.
 - Occurrence of SAEs from first vaccination dose to study end.

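### SAP 11.2.2 gives one injection two dose numbers after a skipped Visit 2, which can put the Dose 2 and Dose 3 safety rows out of step; it also counts adverse events known to precede an injection as following it

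*SAP*

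**What the plan says.** SAP Section 11.2.2 contains three rules that bear on the by-dose safety tables.

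- **Numbering of doses.** "The study dose number is defined in reference to the number of study visits at which vaccination occurred", and "dose 2 corresponds to all vaccinations administered at the second vaccination visit". The section adds that a "vaccination visit is a visit at which study vaccine was administered".
- **Assigning events to doses.** An event belongs to the latest study dose given before it. For an infant who missed a dose and has an event after the next one, "the relative dose of the event will be study dose associated to the subsequent study dose (e.g. dose 3".
- **Same-day events.** An event on a vaccination day goes to that day's dose, "even if the event actually took place before vaccination". The illustration, cut one word short here, is explicit: "if an adverse event begins on the day of the study vaccination but prior to administration of the vaccine, it will be assigned to this" (that is, to the injection given later that day). SAP Section 11.2.1 gives such an event onset day 0.

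Other places matter too. SAP Section 4.2 sets the endpoint as "Occurrence of unsolicited symptoms during the 31-day (Day 0-Day 30) follow-up period after each vaccination". Protocol Section 8.2.1 starts the adverse event period at administration of each dose, while labelling it Day 0 to Day 30. Protocol Section 8.1.1 sends to medical history, and does not count as adverse events, "Pre-existing conditions or signs and/or symptoms present in a subject prior to the first study vaccination". SAP Section 5.2.2.1 foresees an infant vaccinated at Visits 1 and 3 but not at Visit 2: code 1070 removes that infant from the according-to-protocol cohorts. SAP Section 6.4.1 bases the primary safety analysis on the total vaccinated cohort, which keeps the infant.

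**The concern.** The numbering rule counts injections actually given. The missed-dose example appears to count scheduled doses. For an infant who skips Visit 2 and is vaccinated at Visit 3, the two give different labels to the same injection. A programmer who takes N from the study dose number and n from the relative dose would place the event in the Dose 3 numerator and the infant in the Dose 2 denominator. All safety results are descriptive, so the row-level percentages are themselves the result.

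The same-day rule is a separate matter. It covers events whose order is known, as well as those whose order is unknown. An event that began before the injection did not follow that dose, yet it is reported inside the post-vaccination window.

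**Working it through.** **1. Do the two rules conflict?** Take an infant on a 3-dose schedule vaccinated at Visits 1 and 3.

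| Rule in SAP 11.2.2 | Label of the Visit 3 injection |
|---|---|
| Study dose number (count of vaccination visits) | dose 2 |
| Relative dose of its events (the section's example) | dose 3 |

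The schedule has three vaccination visits, so an infant with one missed dose can have at most 3 − 1 = 2 counted doses. A third counted dose after a missed one cannot exist. The example therefore makes sense only under scheduled numbering, which is not the definition at the head of the section.

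**2. Who can be affected?** From the schedule table in SAP Section 6.3.2: 71 (2, 3, 4 months) + 7 (2, 4) + 457 (2, 4, 6) + 66 (3, 5) = 601. Only the 3-dose schedules allow a later vaccination after a skipped Visit 2: 457 + 71 = 528 of 601 (87.9%).

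**3. Size of the mismatch.** The plan gives no figure to reproduce. Assumptions: an equal split, so 528 / 2 = 264 three-dose infants per group; k infants per group who skip Visit 2 and are vaccinated at Visit 3; and the same true event rate p = 30% after every injection. With n labelled by relative dose and N by study dose number:

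- Dose 3 row = p × 264 / (264 − k)
- Dose 2 row = p × (264 − k) / 264

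| k per group | Dose 3 row | Dose 2 row |
|---|---|---|
| 1 | 79.2 / 263 = 30.11% | 78.9 / 264 = 29.89% |
| 5 | 79.2 / 259 = 30.58% | 77.7 / 264 = 29.43% |
| 13 (about 5%) | 79.2 / 251 = 31.55% | 75.3 / 264 = 28.52% |

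The shift is about 0.1 to 1.6 percentage points. The real Dose 2 row also holds the two-dose infants (73 / 2 = 36.5 per group), which dilutes it: at k = 13, 0.30 × 287.5 / 300.5 = 28.70%. The overall/dose row is p × (3 × 264 − k) / (3 × 264 − k) = 30% for every k. With one label for n and N, both dose rows return to 30% for every k.

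There is a visible symptom to look for. If symptom sheets carry the relative-dose label while administered doses are counted, Dose 3 compliance in Template 16 could reach 264 / 259 = 101.9% at k = 5.

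**4. Same-day events.** The event is tied to a visit at which vaccine was given, and that visit is in the denominator, so no n/N mismatch arises. What changes is the classification. On the 2, 4, 6, the 2, 4 and the 3, 5 month schedules (457 + 7 + 66 = 530 of 601, 88.2%) the allowed interval between doses is 52 to 78 days. An event just before a later dose is then outside the previous dose's Day 0 to Day 30 window, and the rule adds a count that would not otherwise be made. For the 71 infants on 2, 3, 4 months (21 to 48 days) it may only move the event from one dose to the next. At dose 1 the medical-history rule in Protocol Section 8.1.1 already catches conditions present beforehand; there is no matching rule for doses 2 and 3.

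**The case against.** **On the dose number.** The governing sentence ties an event to the most recent study dose given, so the event can be read as inheriting whatever label that dose carries. Dose 3 appears only as an example, and no passage says that n and N use different labels. This stands in part: the mismatch is conditional on how the tables are programmed. It does not remove the conflict, because the example cannot be reconciled with the numbering definition. Code 1070 takes these infants out of the according-to-protocol safety cohort, but that analysis is only complementary and is run only if more than 5% of enrolled subjects are excluded from it.

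**On same-day events.** Onset is derived from dates, the windows are written from Day 0, and no section available for review shows that the clock time of onset is collected. Counting same-day events is the cautious direction for safety. Fever or acute disease defers vaccination, and investigators judge causality for everything except solicited local reactions. All of this limits the effect. Minor illness without fever does not defer vaccination, however, and the SAP's illustration covers events whose order is known.

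**Stronger readings that a reader might infer.** One is that numerators and denominators fail to match throughout the by-dose tables. The documents do not support this: the same-day rule causes no mismatch, the overall/dose and overall/subject rows hold, and Templates 18 and 19 use documented doses as N and may match if symptom sheets carry the same label as the events. Another is that the Day 0 and Day 0 to 3 tables are inflated by a calculable percentage. The template list has no Day 0 table, injection-site reactions cannot precede the injection, and temperature is recorded in the evening. Any percentage would rest on an invented time of vaccination and a background rate that the documents do not give.

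**Conclusion.** The point holds in two limited parts.

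First, SAP Section 11.2.2 contradicts itself on the dose number of a Visit 3 injection after a skipped Visit 2. If N follows the study dose number and n the relative dose, the separate Dose 2 and Dose 3 rows of tables such as Template 17 do not match. The shift of about 0.1 to 1.6 percentage points rests on three assumptions: 1 to 13 such infants per group, a 30% event rate, and an equal split. The documents give no count of such infants.

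Second, adverse events known to have begun before that day's injection are classified as following it, against the protocol's collection period and the endpoint. This concerns mainly unsolicited events at doses 2 and 3. Their number is probably small but cannot be estimated from the documents.

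Both groups follow the same rules, so absolute rates are touched more than the comparison between groups. The primary immunogenicity results are not affected. This is a low-severity clarification.

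**What to change.** In SAP Section 11.2.2, define one dose label for the by-dose safety tables and use it for both n and N. The scheduled visit is a natural choice: a Visit 3 vaccination after a skipped Visit 2 is then dose 3 in both. Reword the missed-dose example to agree, and add a footnote that such an infant has received two injections. Template 15 should go on counting the doses actually received. A count of injections given would serve equally well as the label, provided that the example is changed to dose 2.

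For adverse events only, add that where the record shows onset before the injection, the event is listed separately and not tabulated as post-vaccination. Keep the present default where the order is unknown. Leave the same-day rule for medications unchanged, since a prophylactic antipyretic may properly precede the injection.

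The cost is a few sentences and minor programming. The limitation is that same-day events of unknown order remain counted as post-vaccination.
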